**IWRS** 

## 12.5 Glossary of Abbreviations

T //11 1 //	D G 14
Term/Abbreviation	Definition
ANCOVA	analysis of covariance
ANOVA	analysis of variance
AUC	area under the curve
BOTOX ®	Botulinum Toxin Type A Purified Neurotoxin Complex (US adopted name onabotulinumtoxinA), referred to as BOTOX
BUN	blood urea nitrogen
CFR	Code of Federal Regulations
CI	confidence interval
CIC	clean intermittent catheterization
CMH	Cochran-Mantel-Haenszel
CNS	central nervous system
DLPP	detrusor leak point pressure
DRC	Data Review Committee
EBC	expected bladder capacity
eCRF	electronic case report form
EDC	electronic data capture
eGFR	estimated glomerular filtration rate
ELISA	enzyme linked immunosorbent assay
EU	European Union
FDA	Food and Drug Administration
GCP	Good Clinical Practice
HEENT	head, eyes, ears, nose, throat
HIPAA	Health Insurance Portability and Accountability Act
HRQOL	health-related quality of life
ICH	International Conference on Harmonisation
IDC	involuntary detrusor contraction
IDR	independent drug reconstitutor
IEC	Independent Ethics Committee
IRB	Institutional Review Board
IV	intravenous
IVRS	interactive voice response system

interactive web response system

81

LS least squares

MCC maximum cystometric capacity

mITT modified intent-to-treat

NDO neurogenic detrusor overactivity

OAB overactive bladder

PP per protocol
RBC red blood cell
SD standard deviation

SNAP-25 synaptosomal protein of molecular weight 25 kDa

SNARE soluble NSF [N-ethylmaleimide-sensitive factor] attachment

protein receptor

T1 thoracic vertebra level 1
TBS Treatment Benefit Scale

TRPV1 transient receptor potential vanilloid 1

UDS urodynamic studies

US United States (of America)
UTI urinary tract infection

311 WILLIAM WI

**WBC** 

white blood cell

## 12.6 Protocol Amendment 1 Summary

Title: Long-term Extension Study of BOTOX® in the Treatment of Urinary Incontinence Due to Neurogenic Detrusor Overactivity in Patients 8 to 17 Years of Age

Protocol 191622-121 Amendment 1

Date of Amendment: October 2013

### Amendment Summary

This summary includes changes made to Protocol 191622-121 (14 January 2013).

Following is a summary of content-oriented changes that were made to each section of the protocol, and a brief rationale for these changes. Minor editorial and document formatting revisions have not been summarized.

Section	Revision	Rationale
Protocol Title Page	Removed emergency contact number	This information is now included in a study specific contacts page
Investigator signature page	Removed Study Location Added text to ensure all participating personnel are adequately informed about the protocol Removed provision for multiple investigator signatures	Global change to Allergan's protocol template
Synopsis/4.4 Exclusion Criteria/4.5.2 Prohibited Medications/Treatments	Clarified that indwelling catheters are permitted overnight if needed, but that indwelling catheterization is not permitted during diary collection periods	The use of an indwelling catheter overnight is common practice in the patient population intended to be recruited to this study; therefore their use is allowed. However, since the first morning catheterization urine volume is an efficacy parameter, as well as presence or absence of nighttime incontinence, indwelling catheters will not be allowed during diary collection periods.

#### Section

## 4.5.1.1 Definition of Females of Childbearing Potential and Acceptable Contraceptive Methods

4.5.2 Prohibited Medications/Treatments

## 5.9.4 Treatment Procedure

8.6 Early Discontinuation of Patients

9.1.1 Adverse Event

10.1.1 Compliance with Informed Consent Regulations (US 21 CFR Part 50) and Relevant Country Regulations

#### Revision

Removed text relating to females becoming sexually active when postmenarche

Clarified that indwelling catheter was permitted overnight if needed, but that indwelling catheterization was not permitted during diary collection periods

Added text to clarify that patients should remain under observation at the clinic for longer than 30 minutes if local site practice requires this

Clarification added in relation to follow-up in patients who agree to follow-up after exiting the study early.

Additional text regarding the documentation of disease progression/lack of efficacy

Amended wording

#### Rationale

Females who are postmenarche are considered to be of childbearing potential in a biological context; therefore text removed.

The use of an indwelling catheter overnight is common practice in the subject population intended to be recruited to this study; therefore their use is allowed. However, since the first morning catheterization urine volume is an efficacy parameter, as well as presence or absence of night time incontinence, indwelling catheters will not be allowed during diary collection periods.

The protocol provides a minimum time period for observation after treatment; however, local site practice should take precedence if it requires a longer observation period.

[figure not shown]
Clarification regarding time period of follow-up included based on Regulatory Agency feedback.

Global change to Allergan's protocol template

To reflect global change to Allergan's protocol template

вотох

## 12.7 Protocol Amendment 2 Summary

Title: Long-term Extension Study of BOTOX® in the Treatment of Urinary Incontinence Due to Neurogenic Detrusor Overactivity in Patients 5 to 17 Years of Age

Protocol 191622-121 Amendment 2

Date of Amendment: April 2016

### Amendment Summary

This summary includes changes made to Protocol 191622-121 (4 October 2013).

Following is a summary of content-oriented changes that were made to each section of the protocol, and a brief rationale for these changes. Minor editorial and document formatting revisions have not been summarized.

Section	Revision	Rationale
Title and Study Population	Changed minimum age to 5	Updated patient inclusion criterion
Inclusion criteria	Reduced minimum age requirement from 8 years old to 5 years old	Expand age range for inclusion in the study.
Section 5.9.1	Day of Treatment Criteria: added "or presence of significant leukocyturia (e.g. ≥ 30 WBC/HPF)" to the criteria which the investigator should consider when determining if the patient has a UTI	To ensure patient safety, added that in addition to considering patient symptoms, urine culture results and the need for antibiotic treatment, the investigator should also consider the presence of clinically significant leukocyturia when determining if the patient has a UTI. Also provided an example of clinically significant leukocyturia as $\geq$ 30 WBC/HPF.
Section 5.9.3	Use of Anesthesia: added "which could include conscious sedation"	For clarity

		2.3.1 Data Conventions Limited to Diary data	
3.	Disp	osition and Exit Status	14
	3.1	Screening Log Data	14
	3.2	Disposition and Exit Status	14
	3.3	Study Duration	15
	3.4	Protocol Deviations	15
4.	Den	nographics and Other Baseline Characteristics	15
	4.1	Demographics	15
	4.2	Disease Characteristics	15
	4.3	Prior Medications	16
		4.3.1 Prior Anticholinergic Medications for Urinary Incontinence	16
		4.3.2 Antibiotic Medication for Prophylactic Treatment	16
	4.4	Concomitant Medications/Procedures	17
		4.4.1 Concomitant Anticholinergic Medications for Urinary Incontinence	17
		4.4.2 Concomitant Medication	17
		4.4.3 Concurrent Procedures	17
	4.5	Past Medical History	17
5.	Effic	eacy Analyses	17
	5.1	Collection of Key Efficacy Measurement and Derivation of Key Efficacy Van	
	_		
	5.2	Key Efficacy Analyses	18
	5.3	Other Efficacy Analyses	18

		5.3.1	Analysis of the Number of Patients that have Reduction from Baseline Daytime Urinary Incontinence Episodes that meet Certain Thresholds	
		5.3.2	Urine Volume at First Morning Catheterization (mL)	
		5.3.3	Presence or Absence of Night Time Urinary Incontinence	
		5.3.4	Duration of effect	
		5.3.5	Modified Treatment Benefit Scale (TBS)	
6.	Safet	y Analy	yses	21
	6.1	Study	Treatment – Exposure and Administration	21
		6.1.1	Exposure to Study Treatment(s)	21
		6.1.2	Administration of Study Treatment(s)	22
	6.2	Adver	se Events	22
		6.2.1	Potential Distant Spread of Toxin Adverse Events (applicable to BOTO	X®
	_		studies only)	24
8.	Healt	h Outc	omes Data Analyses	30
9.	Interi	m Ana	lyses	30
10.	Analy	ysis for	US FDA	30
11.	Data	Collect	ted but not Analyzed	31
12.	Devia	ations f	rom Protocol	31
13.	Refer	ences		31

List of Tables

Table 1	BOTOX Treatment Groups Based on Actual Dose Administered
Table 3	Initial Imputed Date Algorithm

1. Introduction

This document details the planned analyses for study 191622-121. Patients that complete study 191622-120 are eligible to enroll into study 191622-121. The purpose of study 191622-121 is to further evaluate the long-term safety and efficacy of BOTOX for the treatment of urinary incontinence due to neurogenic detrusor over activity (NDO) in patients 5 to 17 years of age.

When all patients in study 191622-120 exit the study, there will be a data base lock (DBL) for study 191622-120 and a subsequent interim DBL and CSR for study 191622-121. The second and final analysis will occur when all patients exit study 191622-121. A final CSR will be completed at this time.

Data from Study 191622-121 will be integrated with the corresponding patient data from their participation in the preceding Study (191622-120). Patients who have received at least 1 BOTOX treatment since the start of their overall clinical study participation, i.e. either in study 191622-121 or the preceding study 191622-120, will be included in the analysis. This BOTOX-treated population will be used for all the statistical analyses and results presented by BOTOX treatment cycle. Patients who participated only in Study 191622-120 and did not participate in Study 101622-121 will not be included.

On completion of the interim analysis, the study will be unblinded to Allergan personnel. Study sites will be unblinded upon finalization of the interim clinical study report.

1.1 Primary Study Objectives and Design

The objective of study 191622-121 is to evaluate the long-term safety and efficacy of BOTOX for the treatment of urinary incontinence due to NDO in patients 5 to 17 years of age who have not been adequately managed with anticholinergic therapy.

This is a long-term extension study to the preceding study, 191622-120. Patients will roll over directly from the preceding study; the exit visit of study 191622-120 is also the entry visit for study 191622-121. Patients exit study 191622-120 once they have qualified for retreatment or at week 48 if they never qualified. For the first retreatment in study 191622-121, the qualification may have occurred in study 191622-120.

In this study, patients can receive multiple injections of the following doses:

- 50 units (U) BOTOX (not to exceed 6 U/kg)
- 100 U BOTOX (not to exceed 6 U/kg)
- 200 U BOTOX (not to exceed 6 U/kg)

In order to ensure that the upper dosing limit of 6 U/kg is not exceeded, the actual dose administered is adjusted based on patient weight, if necessary.

The dose received at any given treatment will be determined by the investigator based on the response to the preceding blinded treatment. The investigator can elect to keep the dose the same or increase the dose compared to the preceding treatment. If it is deemed a decrease in dose is warranted, the patient would be exited from the study. The actual dose received remains blinded unless the patient is requested to exit the study via the IVRS, as described at the end of Section 5.5 of the protocol or until the interim analysis of this study has been reported.

Patients in this study are evaluated at scheduled visits at 2, 6, and 12 weeks after each retreatment (week 2, 6 and 12 visits). After week 12 visit (12 weeks from the re-treatment), there are alternating telephone and clinic visits every 6 weeks until they qualify for further retreatment or exit the study. Request for retreatment can occur at any scheduled clinic or telephone visit, or between scheduled visits. If a request occurs at a scheduled clinic visit, this then becomes a qualification for retreatment visit, otherwise a qualification for retreatment clinic visit should occur within approximately 1 to 2 weeks of request.

Patients exit this study once 48 weeks have elapsed from the time of entry into the study and at least 12 weeks follow-up has occurred after their last BOTOX injection. Hence, for patients that did not prematurely exit the study, the study exit will be between 48 and 60 weeks after entry into this study; the latter being for patients who received retreatment at Week 48.

The efficacy measure that is of key interest is daytime urinary incontinence episodes, and the key time point is week 6 after each treatment.

1.1.1 Sample Size

For this long-term extension study, no formal sample size calculation was used. Approximately 78 patients are anticipated to roll over into this study, which is assuming approximately 76% of patients randomized into Study 191622-120 will be available and willing to participate in this study.

1.2 Secondary and Other Objectives

Not applicable.

1.3 Experimental Unit and Analysis Unit

The experimental unit in this study is a study subject. The efficacy measure of key interest is daytime urinary incontinence episode measured at a subject level.

2. Analysis Populations and Data Conventions

In order to maintain blinding of the BOTOX dose received, the drug is reconstituted by an independent drug reconstitutor (IDR). Study drug accountability and reconstitution records are then reviewed and confirmed by independent drug monitors (IDM). If an incorrect dose was administered, the IDM will trigger completion of the "Incorrect Unit Dose Administered" form by the IDR and the "incorrect unit dose administered" will be entered into the electronic case report form (eCRF).

2.1 Analysis Populations

One analysis population will be used in the statistical analysis of this study namely, the BOTOX-treated population.

BOTOX-treated population will include all patients that enrolled into study 191622-121 after receiving BOTOX injection in study 191622-120. A patient is considered to have enrolled in study 191622-121 if in study191622-120, in the extension eCRF page, it is marked that a patient will continue into study 191622-121.

Actual Dose Administered	BOTOX Treatment Group
<75 U	50 U BOTOX
75 U ≥ and < 150 U	100 U BOTOX
≥ 150 U	200 U BOTOX

Table 1 BOTOX Treatment Groups Based on Actual Dose Administered

For cycle based analysis, since the patient's dose can be increased in a blinded fashion from one cycle to the next, the analysis will be based on actual treatment received during that cycle and will be assigned to the nearest dose group per Table 1 above. As a result of either the 6 U/kg weight cap or site error, patients may not receive the dose assigned per the IWRS (interactive web response system).

Patients will be assigned to actual treatment groups for analysis purposes as follows:

- 1. If the "incorrect unit dose administered" is populated in the eCRF, this dose will be used and adjusted per Table 1 above.
- 2. If the "incorrect unit dose administered" is not populated in the eCRF, then the randomized dose per IWRS (ie, 50U, 100U, or 200U) and the patient's weight at the qualification for retreatment visit will be utilized to determine the actual dose administered as described in section 12.1 of the study protocol. The dose administered will then be adjusted per Table 1 above.

For analysis that is not cycle based (e.g. baseline and disease characteristics), the summary will be by the overall BOTOX -treated population and by what the BOTOX- treated patients received in Cycle 1, which also coincides with the Study 191622-120 safety treatment groups. In this document these treatment groups will be referred to as Cycle 1 treatment groups.

2.1.1 Handling Mis-randomization and Mis-stratification

Treatment group assignment, in case of patients who received incorrect dose is discussed in Section 2.1 above.

2.2 Analysis Visit Windows

All by visit analysis will be by visit window. The target day and visit window for each treatment cycle will be referenced to days after treatment/injection. The visit window for each treatment cycle is defined as follows:

[(target day of current visit + target day of previous visit)/2+1] to [(target day of current visit + target day of next visit)/2]

For safety variables if there are multiple assessments in a given window, the value collected from the visit closest to the target day will be used to represent the window. If, instead of a single closest visit, 2 visits with values are equidistant (but not on the same day) from the target day, the latest visit will be used. If there are multiple observations on the same day the average of the observations will be used. For laboratory variables, this rule will be applied separately for each laboratory parameter.

2.3 Data Conventions

The following data conventions will be applied to all analyses.

- Baseline and study baseline are used interchangeably throughout this document. They both refer to baseline information collected at the start of study 191622-120.
- In general, metric systems will be used (e.g., kilograms (kg) and centimeters (cm)) and clinical laboratory data will be presented with the Standard International (SI) units.
- The variance for Kaplan-Meier estimates will be calculated using Greenwood's formula.

- Descriptive statistics for continuous variables include the sample size (n), mean, SD, median, minimum (min), first quartile (Q1), third quartile (Q3), and maximum (max).
- Summary statistics for categorical variables include the sample size (n), frequency count and percent.
- The Medical Dictionary for Regulatory Activities (MedDRA) dictionary will be used to code all adverse events (AEs) and medical histories.
- World Health Organization Drug Dictionary Enhanced (WHO DDE) preferred name and MedDRA will be used to code all medications.
- Cumulative study duration from Day 1 (first injection date in preceding study 191622-120) will be calculated as:

Study day in study = visit date - day 1 date + 1.

 Cycle duration for a given Treatment X (i.e., Xth injection cycle where X > 1)will be calculated as:

Study day of cycle X = visit date - day 1 of Treatment X + 1.

- The algorithm presented in Table 3, together with the rules below will be used to impute incomplete or missing dates for adverse events and medications as follows:
 - (a) AE start dates will be imputed as the minimum of the following:
 - initial imputed date, where target date = first study drug injection date if the AE started in study 191622-120; exit day in study 191622-120 if the AE started in study 191622-121.
 - complete end date
 - (b) Medication start dates will be imputed as the minimum of the following:
 - initial imputed date, where target date = first study drug injection date 1 if the medication started in study 191622-120; exit day in study 191622-120 if the medication started in sudy 191622-121.
 - complete end date
 - (c) AE and Medication end dates will be imputed as the minimum of the following:

- initial imputed date, where target date = study exit date + 30. The exit date to be used will depend on when the AE (or medication) ended. If it ended in study 191622-120, the study 191622-120 exit date will be used. In contrast, if it ended in study 191622-121, the study 191622-121 exit date will be used.
- death date
- Concurrent medication will be classified using the following convention: 1) If the start date of medication is after or on study drug injection date, then it will be counted as concomitant medication; 2) If the start date of medication is prior to the study drug injection date and stop date is on or after study drug injection date, then it will be counted as both prior medication and concomitant medication.
- All partial dates (including AE, concurrent and prior medication) will be listed "as is" in the data listings.

[figure not shown]
Table 3 Initial Imputed Date Algorithm

Available Year	Available Month (MM)			
(YYYY)	Missing	< Target Month	= Target Month	> Target Month
Missing	Target Date			
< Target Year	YYYY-12-31	YYYY-MM-LD		
= Target Year	Target Date	YYYY-MM-LD	Target Date	YYYY-MM-01
> Target Year	YYYY-01-01	YYYY-MM-01		

[figure not shown]

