# 5.5 Method for Assignment to Treatment Groups/Randomization

There will be no randomization in this long-term extension study.

All patients who receive treatment in this study will receive BOTOX. The blinded dose received (50, 100, or 200 U BOTOX, not exceeding 6 U/kg) will be dependent on the assessment of the clinical response (efficacy and safety) to the previous blinded study treatment (which will have been 50, 100, or 200 U BOTOX, not exceeding 6 U/kg). The patient/parent/caregiver will be questioned on their treatment response to establish if, in their opinion, the current treatment response is adequate or if there was little or no treatment benefit and whether they would be willing/want to have a higher dose. They will also be questioned on whether the patient is experiencing side effects. Using this information, the investigator will use his/her own clinical assessment of the patient and apply the following criteria for the retreatment dose request:

- if the benefit/risk balance is evaluated by the investigator to be appropriate at the current dose, then the same dose would be requested
- if the investigator assessed that, although the preceding dose was well tolerated, the
  response received was insufficient and warrants a higher dose, then a dose increase would
  be requested

• if the investigator assessed that there were side effects that would warrant a lower dose, the patient would be exited from the study

Compared to the previous treatment, the investigator therefore has the following options:

- elect to keep the same dose as received at the previous treatment (not to exceed 6 U/kg)
- elect to increase the dose compared to the previous treatment (not to exceed 6 U/kg):
- if the patient received 50 U BOTOX at the previous treatment, they would receive 100 U BOTOX
  - if the patient received 100 U BOTOX at the previous treatment, they would receive 200 U BOTOX
  - if the patient received 200 U BOTOX at the previous treatment, they would remain at 200 U BOTOX (after 2 requests to increase the dose from 200 U the patient will be exited; see below)

At the qualification for retreatment visit the investigator or designee will contact the IVRS/IWRS and indicate the treatment option for the patient. IVRS/IWRS options will be either to remain at the same dose or to increase the dose since patients will be exited from the study if the investigator assessed that a lower dose was warranted (see below).

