#### 9.1 Definitions

#### 9.1.1 Adverse Event

Any untoward medical occurrence in a patient or clinical investigation patient administered a pharmaceutical product and that does not necessarily have a causal relationship with this treatment. An adverse event can therefore be any unfavorable and unintended sign (including an abnormal laboratory finding), symptom, or disease temporally associated with the use of a medicinal (investigational) product, whether or not related to the medicinal (investigational) product.

Note: Adverse events must be collected once informed consent has been obtained, regardless of whether or not the patient has been administered study drug.

Progression of NDO, including new or worsening of anticipated clinical signs or symptoms, which are collected as clinical efficacy variables and assessed as unequivocally associated with the disease progression and /or lack of efficacy, should not be reported as adverse events unless the disease progression is greater than anticipated in the natural course of the disease.

Adverse events will be assessed, documented, and recorded in the eCRF throughout the study (ie, after informed consent/assent has been obtained). At each visit, the investigator will begin by querying for adverse events by asking each patient or parent/caregiver a general, non-directed question such as "How have you been feeling since the last visit?" Directed questioning and examination will then be done as appropriate. All reported adverse events will be documented on the appropriate eCRF.

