6.2 Adverse Events

Adverse events (AEs) will be coded by system organ class and preferred term using the Medical Dictionary for Regulatory Activities (MedDRA).

Pre-treatment AEs are AEs that have start date on or after the signing of consent form and prior to the first BOTOX injection.

An AE will be considered a cycle 1 treatment-emergent adverse event (TEAE) if it fulfills one of the conditions below:

• the start date of the AE is on or after the 1st BOTOX injection and prior to the date of the 2nd BOTOX injection

• the AE started before the 1st BOTOX injection and increased in severity or became serious during the cycle (from date of 1st BOTOX injection to the day before the 2nd injection).

For subsequent cycles (cycle's number > 1) an AE is considered a TEAE in the current cycle if it fulfills one of the conditions listed below.

- the AE start date is within the cycle i.e., it is on or after the date of the cycle injection and prior to the date of the next injection
- the AE has increased in severity or became serious during the current cycle

The incidences of TEAEs will be summarized by BOTOX treatment cycle.

The number and percentage of patients reporting TEAE in each treatment group will be tabulated by descending percentage in any group, by system organ class and preferred term, and further categorized by severity and causal relationship to the study drug and study drug injection procedure. If more than 1 AE is coded to the same patient, the patient will be counted only once for that preferred term using the greatest severity for the summarization by severity and causal relationship.

The number and percentage of patients who have treatment-emergent serious adverse events (TESAE) will be summarized by system organ class, preferred term and treatment group. Similar summary will be presented for patients with TEAE leading to discontinuation from the study. In addition, separate patient listings will be generated for deaths, SAEs, and TEAEs leading to study discontinuation.

In addition, the incidence of TEAEs, SAEs, study drug/study injection procedure related TEAEs, deaths and TEAEs leading to study discontinuation will be reported for the overall study period.

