All the summaries discussed above will be based on all AEs observed during the entire cycle. Since the design of this study allows patients to request/receive retreatment from week 12 (day 84) onward, an additional summary showing the number and percentage of patients with TEAEs by preferred term and treatment group in descending order of incidence will be presented for the TEAE observed prior to or on day 84 after each injection cycle. This will allow for a comparison across dose groups for the same duration of time (ie, since patients can request retreatment from week 12 onwards, patients remain in a cycle for varying time periods). Therefore this analysis provides a more direct comparison across dose groups.

In addition, the number and percentage of patients who have a treatment-emergent UTI during the first 2 weeks (14 days), the first 12 weeks (84 days), and during the overall treatment cycle will be presented by the treatment received in each treatment cycle.

The number of UTI events per patient year will be summarized for the six month prior to screening and for each BOTOX treatment cycle. The number of UTI events per patient year, for the BOTOX treatment cycle, is defined as follows: (The sum of all the patients UTI events)/ (The sum of all the patients duration in years during the BOTOX treatment cycle). The number of UTI events per patient year for the 6-months prior to screening is similarly defined. All patients will be included in these analyses irrespective of whether they experienced a UTI or not.

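### Incomplete AE start dates in 191622-121 are imputed without reference to the extension injections, so events can be placed in an earlier treatment cycle

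*SAP*

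**What the plan says.** SAP Section 2.3 imputes an AE start date as the earlier of the Table 3 date and any complete end date. Table 3 works from a target date. For AEs that began in 191622-120 the target is the first injection date. For AEs that began in the extension it is the "exit day in study 191622-120 if the AE started in study 191622-121". Protocol Section 3 makes that exit visit the same as extension day 1. The same SAP section adds, for the data listings, that "All partial dates (including AE, concurrent and prior medication) will be listed" as recorded.

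SAP Section 6.2 uses the start date to place an AE in a cycle. Cycle 1 requires that "the start date of the AE is on or after the 1st BOTOX injection and prior to the date of the 2nd BOTOX injection", and later cycles run likewise from their own injection to the next. The other route into a later cycle is that "the AE has increased in severity or became serious during the current cycle". Results are reported by cycle and by the dose received in it. They include a table of each "TEAE observed prior to or on day 84 after each injection cycle" and counts of patients with "treatment-emergent UTI during the first 2 weeks (14 days), the first 12 weeks (84 days), and during the overall treatment cycle".

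On dose, Protocol Section 5.5 says that "IVRS/IWRS options will be either to remain at the same dose or to increase the dose".

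**The concern.** The imputation rule and the cycle windows do not fit together. Cycles are bounded by injection dates, but for extension events the rule looks only at the day the patient left the first study. For events in 191622-120 the rule does anchor on the injection.

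An event that followed an extension injection can therefore be counted in the cycle before it. The assigned dose can only stay the same or rise, so the event is credited to an equal or lower assigned dose. The outputs exposed are the by-cycle AE tables, the 14-day and 84-day UTI tables, the UTI rate per patient-year by cycle, and the day-84 table, which the SAP offers as its fairer comparison between doses.

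**Working it through.** The plan gives no figure to reproduce, so the check applies the rule as written.

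**1. What Table 3 returns when the target is the exit day**

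| Known part of the start date | Imputed start |
|---|---|
| Nothing | Exit day |
| Exit year only | Exit day |
| Exit year and exit month | Exit day |
| A later month, with its year | 1st of that month |
| A later year only | 1 January of that year |

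Capping at the end date can only move these earlier. The Protocol Summary allows up to 28 days from qualification to injection, and patients who entered without qualifying are injected later still. The exit day is therefore normally in Cycle 1.

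**2. A worked patient (invented dates).** Injection 1 on 1 March 2016, exit 10 August 2016, injection 2 on 31 August 2016, injection 3 on 18 January 2017.

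- Onset 3 September 2016 (Cycle 2), date missing or year only: imputed 10 August, Cycle 1.
- Onset 31 August 2016 (Cycle 2), month known: imputed 10 August, Cycle 1.
- Onset 20 January 2017 (Cycle 3), month known: imputed 1 January, Cycle 2.
- Onset 5 October 2016 (Cycle 2), month known: imputed 1 October, Cycle 2, which is correct.

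The imputed 10 August is study day 163 of Cycle 1. Those events leave the day-84 table and, if UTIs, the 14-day and 84-day counts. More generally, 84 days elapsed puts the exit day at study day 85 or later, provided 191622-120 used the same 12-week minimum. These documents do not state that.

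**3. Day missing, onset soon after an extension injection.** The event is misplaced if onset falls in the injection month and the injection was not on the 1st. For onset 0 to 13 days after injection the mean lag is 6.5 days, so the share is about 1 − 6.5/30.4 − 12/365.25 = 0.786 − 0.033 = 0.753. Enumeration over every injection day in 2015 to 2018 gives 0.754. For 0 to 27 days it gives 0.524, and for 0 to 83 days 0.175.

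**4. Share of all extension AEs put in an earlier cycle.** Assumptions: exit dates uniform over 2015 to 2017, onset uniform over follow-up, 30,000 AEs per pattern and date type. The patterns are:

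- A: first extension injection 7 to 28 days after entry, then every 12 to 24 weeks, up to 4 injections.
- B: same start, then every 24 to 40 weeks, up to 2.
- C: same start, one injection only.
- D: entered unqualified, one injection on day 28 to 300.

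| Date type | A | B | C | D |
|---|---|---|---|---|
| Day missing | 0.124 | 0.087 | 0.046 | 0.045 |
| Year only | 0.797 | 0.702 | 0.533 | 0.373 |
| Fully missing | 0.952 | 0.949 | 0.947 | 0.518 |

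None moves to a later cycle. The fully missing row is simply the share of AEs that began after an extension injection: all of these move.

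**5. Early-onset events.** If the AE hazard is 5 times higher on days 0 to 13 (assumed), the day-missing row becomes 0.321, 0.249, 0.146 and 0.142. The 14-day count of day-missing AEs in extension cycles is then 0.39 to 0.41 of the true count, and the 84-day count 0.67 to 0.71. With uniform onset the 14-day count is 0.97 to 0.99 of true, because later onsets in the same cycle are also pulled forward to the 1st of their month.

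**The case against.** The rule is often right. An event between entry and the first extension injection belongs in Cycle 1, as does any event in a patient never retreated. An event known only to an injection month may precede that injection. With onset uniform over a month later than the exit month, 48% are misplaced and 52% are correct. If the first extension injection falls on the exit day, the target itself lies in Cycle 2.

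Few dates may be incomplete. Under Protocol Section 9.1.1, "At each visit, the investigator will begin by querying for adverse events", and visits are frequent. Assume 100 to 500 extension AEs, 1% to 5% of them missing the day. The number moved is then between 100 × 0.01 × 0.045 = 0.05 and 500 × 0.05 × 0.124 = 3.1, or between 0.1 and 8.0 with the 5-fold hazard. Year-only and fully missing dates, where the shares are largest, should be the rarest.

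The consequences are also bounded. There is no hypothesis testing, and dose follows earlier response, so contrasts between doses are confounded anyway. Overall-study incidence is unchanged, the listings keep partial dates, and events that worsen or become serious still count in the later cycle. The SAP amendment log describes the rules as the company standard.

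All of this limits the size and stands. It does not make the attribution correct: the error runs in one direction only and affects tables built to compare cycles and doses. The objection that anchoring on the injection inflates the 14-day count also stands, and the fix has to allow for it.

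**Conclusion.** The concern holds. As written, the rule places fully missing, exit-year-only and injection-month start dates without regard to extension injections. Whenever it gets the cycle wrong, the cycle is an earlier one with an equal or lower assigned dose. Most dates missing only the day stay in the right cycle; the exposure is concentrated in events soon after an extension injection.

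The percentages rest on assumed retreatment patterns and onset distributions. The fall of the 14-day count to about 40% of true depends on the 5-fold early hazard, which the documents do not support or exclude. The number of incomplete dates is not given, so the total effect cannot be sized and may be small. The rule should be corrected because it is inconsistent with Section 6.2 and the correction is cheap, not because a large bias has been shown.

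**What to change.** Amend SAP Section 2.3 for AEs that started in 191622-121:

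1. Impute the start to an extension injection date if the known year and month cover that injection, any complete end date is on or after it, and the AE was first reported after that treatment visit. Otherwise keep Table 3.
2. Where the date is fully missing or known only to the year and fits more than one cycle, bound onset by the visit of first report. Impute to the last injection before that visit that agrees with the known date parts. List these AEs with all candidate cycles as a sensitivity check.
3. Show the 14-day UTI table with and without AEs whose day was imputed.

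The cost is a short SAP amendment, some programming, one listing and one repeated table. The date of first report must be derivable from the eCRF, which the documents do not state. Without that condition, anchoring on the injection month would move 3% to 11% of day-missing AEs to too late a cycle. With it, every day-missing AE falls in the right cycle, provided each is reported at the next visit.

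The price is that anchored events land on the injection day. The 14-day count of day-missing AEs would then be overstated: about 1.2 times true with the 5-fold early hazard and 2.0 times with uniform onset. That is why item 3 is needed.
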